4.1.5 PD Population

All patients who are included in the safety population and have at least baseline and 1 post-dose PD assessment will be included in the PD population. This population set will be derived from sample collection date for Vitreous Humor sample collected at screening and undiluted vitreous/Aqueous humor sample at time of surgery.

All PD analyses will be based on the PD population.

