9.3.3 PD Analyses

Pharmacodynamic statistical analyses will be conducted based on the proteomic analysis of cytokine biomarkers in ocular fluids.

Vitreous and aqueous humor sample results and changes from baseline will be summarized by treatment group. Treatment effect will be assessed within and between treatment groups using an appropriate statistical method. The analysis will be based on log-transformed data if required.

Measurements below or above the limits of detection will be censored at the laboratory reported lower or upper limit of detection. Analytes will not be included in the analyses if more than half of the measurements in a treatment group are below the limit of detection.

Further exploratory analyses may be performed to evaluate potential dose-related measures.

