After signing informed consent and meeting all eligibility criteria, patients will undergo a vitreous tap for cytokine and other potential molecular biomarker analysis followed by a single intravitreal injection of ONL1204. This will occur on the day of diagnosis (Day 1). Safety visits will be conducted 1-day post-injection and per Investigator's discretion until Visit 3. At Visit 3 (3+ days post-injection, in accordance with standard of care) patients will undergo surgical repair of their retinal detachment with vitrectomy (with or without scleral buckling) and gas or oil tamponade. At the time of surgery, an undiluted vitreous sample will be collected for pharmacokinetic and pharmacodynamics analyses, and an aqueous sample will be collected for pharmacodynamic analysis. Additional safety visits will be conducted 1-day post-surgery, 14 (+4 days) days post-surgery, Weeks 6, 9 (±7 days each), and Week 24 (±14 days; study exit).

As this is a first-in-human safety study of ONL1204, the first patient in the first cohort will receive the lowest dose of ONL1204. After this patient completes Visit 5 (14 +4 days post-surgery) and a safety review committee reviews the data, the remainder of the patients in that cohort will be enrolled. After all patients in the cohort have completed Visit 5, the SRC will review the available safety data to determine if dose limiting toxicity exists that prohibits enrolling the next higher dose cohort. This process will be repeated until escalating to the top dose.

The following doses will be evaluated: 25 μ g, 50 μ g, 100 μ g, and 200 μ g ONL1204. ONL1204 ophthalmic solution is available in vials with concentrations of 0.5 mg/mL and 2 mg/mL. Therefore, a volume of 0.05 or 0.1 mL will be injected into the study eye.

Objectives

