- Baseline: The baseline value is defined as the last available valid (quantifiable continuous or categorical value), non-missing observation for each participant prior to first study drug administration. Repeat and unscheduled assessments will be included in the derivation of the baseline values.
- Change from Baseline: The change from baseline value is defined as the difference between the result collected/derived at a post-baseline visit/time point and the baseline value.

The change from baseline value at each post-baseline visit/time point will be calculated for all continuous parameters using the following formula:

Change from Baseline Value = Result at Visit/Time Point – Baseline Value

The change from baseline value will only be calculated if the specific post-baseline visit/time point result and the baseline value for the parameter are both available and will be treated as missing otherwise.

• Study day: The study day of an event is defined as the relative day of the event starting with the date of the first study drug administration (reference date) as Day 1 (there will be no Day 0).

The study day of events occurring before the first study drug administration will be calculated as:

Study Day = (Date of Event - Date of First Study Drug Administration)

For events occurring on or after Day 1, study day will be calculated as:

Study Day = (Date of Event - Date of First Study Drug Administration) + 1

Study days will only be calculated for events with complete dates and will be undefined for events that are 'Ongoing' at the end of the study.

Relative days compared to an alternative reference point will be calculated similarly, but the alternative starting reference start date will be used instead of the date of the first study drug dosing.

- Prior Medications: Prior medications are defined as any medication where the use was stopped prior to the first administration of the study medication.
- Concomitant Medications: Concomitant medications are defined as any medication (other than the study drug) that was used at least once after the first administration of the study drug. Medications that were stopped on the same date as the first study drug administration will be defined as concomitant medications. If a clear determination cannot be made (partial medication end dates) the medication will be classified as concomitant.

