11. PHARMACODYNAMICS

Pharmacodynamic statistical analyses will be conducted based on the proteomic analysis of cytokine biomarkers in ocular fluids.

The following PD endpoints will be assessed:

- Vitreous Humor sample collected at pre-injection baseline by vitreous tap
- Vitreous Humor sample from the undiluted sample collected at the time of surgery
- Aqueous Humor sample collected at the time of surgery

Analyte concentrations will be provided for the vitreous humor and aqueous humor samples.

All PD endpoints will be analyzed separately by ONL Therapeutics.

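### SAP 4.1.5 requires a baseline sample for every PD analysis, so a patient with no baseline tap collected drops out of surgery-time summaries that need no baseline

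*SAP*

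**What the plan says.** **Entry rule.** Under SAP 4.1.5, safety-population patients who "have at least baseline and 1 post-dose PD assessment will be included in the PD population". Membership is worked out from dates, not assay results: "This population set will be derived from sample collection date for Vitreous Humor sample collected at screening", together with the vitreous or aqueous sample taken at surgery. The section then applies the rule without exception: "All PD analyses will be based on the PD population".

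**Planned analyses.** Protocol 9.3.3 says: "Vitreous and aqueous humor sample results and changes from baseline will be summarized by treatment group". It also foresees an assessment of treatment effect within and between dose groups. SAP 11 names three PD endpoints: the pre-injection vitreous tap, "Vitreous Humor sample from the undiluted sample collected at the time of surgery", and "Aqueous Humor sample collected at the time of surgery".

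**Change from baseline.** SAP 3 (Key Definitions) has its own safeguard: "The change from baseline value will only be calculated if the specific post-baseline visit/time point result and the baseline value for the parameter are both" present; otherwise the change is treated as missing.

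**Who should have a baseline.** Everyone, by design. In SAP 1, "patients will undergo a vitreous tap for cytokine and other potential molecular biomarker analysis followed by a single intravitreal injection of ONL1204".

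**The concern.** Protocol 9.3.3 plans two kinds of PD summary, levels and changes. Only changes need a baseline, yet SAP 4.1.5 demands one for both. A treated patient with no baseline vitreous sample collected loses two of the three PD endpoints in SAP 11 from all grouped analyses, even when both surgery samples were taken and assayed.

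The aqueous endpoint shows this most clearly. SAP 11 and the schedule in Protocol 4.3 have aqueous only at surgery, so on that reading no aqueous change can be computed for anyone. A missing vitreous tap still removes the patient's aqueous result. (Protocol 6.4.2 also mentions an anterior chamber tap at baseline. The two places should be reconciled, but surgery-time levels need no baseline either way.)

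What is at stake is part of a small exploratory data set. Cohorts have 4 patients, and Protocol 2.2 expects the PD results to contribute to Phase 2 dose selection. A lost patient is not made up: replacement (Study Summary; Protocol 6.8) covers only patients who were not injected, or who left before Visit 4 for reasons unrelated to treatment.

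**Working it through.** The plan states no figure for this, so there is none to reproduce. The check is a reading of the sections against each other, then a simple count.

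**1. Does each planned summary need the baseline?**

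| Summary | Needs a baseline? | Already protected elsewhere? | Effect of SAP 4.1.5 |
|---|---|---|---|
| Vitreous change from baseline | Yes | Yes, SAP 3 sets it to missing if unpaired | None |
| Vitreous level at surgery | No | Not needed | Patient left out |
| Aqueous level at surgery | No | Not needed | Patient left out |

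The baseline requirement is redundant in the first row and only loses data in the other two. The rule also works in reverse: a patient with a baseline tap but no surgery sample leaves the baseline summary.

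**2. Comparison within the SAP.** The ocular PK population (SAP 4.1.4.1) asks for a quantified vitreous drug level in a safety-population patient and no baseline. The undiluted vitreous specimen taken at surgery serves both PK and PD (Protocol 4.3; SAP 1). The same specimen can therefore count for ocular PK and be left out of PD.

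**3. Size of one loss.** Input: 4 patients per cohort, 4 cohorts, 16 in total (Protocol, Study Schematic). With m patients left out and the same SD, the standard error of the cohort mean grows by √(4/(4−m)).

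- m = 1: 1/4 = 25% of the cohort; √(4/3) = 1.155, about 15% larger.
- m = 2: 2/4 = 50% of the cohort; √(4/2) = 1.414, about 41% larger.

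**4. How likely is a loss?** The documents give no rate of uncollected taps. Taking p as an assumption, with patients independent, P(at least one of 4) = 1 − (1−p)^4:

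| Assumed p | Given cohort loses ≥1 | Expected losses among 16 (16p) |
|---|---|---|
| 5% | 1 − 0.95^4 = 18.5% | 0.8 |
| 10% | 1 − 0.90^4 = 34.4% | 1.6 |
| 20% | 1 − 0.80^4 = 59.0% | 3.2 |

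**5. After the change.** A cohort with one uncollected tap keeps 4 of 4 patients in the surgery-time summaries instead of 3 of 4, provided all four have surgery samples. With two uncollected taps it keeps 4 instead of 2. The n for change from baseline stays at 3 or 2.

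**The case against.** The best defence is that the PD question is a paired one. Protocol 1.3.3 describes looking at cytokines before dosing and again some days later, and a population with both samples keeps the same patients at every time point. That is a fair reason to restrict the change analysis. It does not justify restricting the levels, which Protocol 9.3.3 and SAP 11 list separately.

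Several limits on the point do stand:

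- **Narrow trigger.** Membership follows collection date, so a baseline sample that was collected but could not be assayed still qualifies the patient. Only a tap with no sample collected excludes. The tap is planned for every patient, and Protocol 1.3.3 regards it as a routine procedure.
- **Who does the analysis.** SAP 11 leaves the PD endpoints to a separate analysis by the sponsor, and the legible titles in the SAP table and listing indexes include no PD output. The harm arises only if that separate work follows SAP 4.1.5. The text says it does, and no other population is named for it.
- **Exploratory status.** There is no hypothesis test, and the primary objective concerns the MTD and doses for Phase 2.

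Three stronger readings are tempting but not supported:

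- **That the data are thrown away.** SAP 4.1.1 puts listings on the ITT population, and SAP 11 says analyte concentrations will be provided. The listing index shows no PD analyte listing, so this is only a partial mitigation, but nothing says results are deleted. They are left out of grouped analyses.
- **That the SAP departs from the protocol without declaring it.** Protocol 9.1.3 defines no PD population and SAP 15 reports no change, but Protocol 9.3 leaves the description of analysis populations to the SAP.
- **That a widened confidence interval measures the damage.** Neither document specifies an interval for a PD mean. SAP 3 plans n, mean, SD, median, minimum and maximum.

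**Conclusion.** The point holds as a contingent flaw in a population definition for exploratory endpoints. As written, SAP 4.1.5 leaves out of the surgery-time vitreous and aqueous analyses any treated patient with no baseline vitreous sample collected, and gains nothing for the paired analysis in return. Each such patient costs a cohort a quarter of its surgery-time summary and about 15% in the standard error of the mean, assuming an unchanged SD. The chance that a given cohort is affected is about 19%, 34% or 59% at 5%, 10% or 20% uncollected taps; these rates are assumptions. If every tap yields a sample, the baseline requirement removes nobody from the surgery-time summaries. The primary safety analyses are untouched. It is a cheap improvement worth making, not a threat to the trial's main conclusions.

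**What to change.** Reword SAP 4.1.5 so that the PD population is all Safety Population patients with at least one evaluable PD sample. State that each fluid and time point is summarised on all available samples, that only change from baseline is limited to patients with paired vitreous samples, and that both n values are shown. Say that the sponsor's separate PD analysis follows the same definition. Reconcile Protocol 6.4.2 with the schedule in Protocol 4.3 and with SAP 11 on whether aqueous fluid is sampled at baseline.

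The cost is SAP wording, plus the protocol reconciliation, with no new samples or assays. The one drawback is that n can differ between the by-time-point and paired summaries, so a reader cannot subtract one mean from the other to obtain the mean change. Showing both n values makes this visible.

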5. PARTICIPANT DISPOSITION AND ANALYSIS POPULATIONS

Participant disposition and analysis population will be based on the ITT population. Participant disposition and analysis populations will be summarized descriptively as described in $\frac{\text{section } 3.1}{(\text{categorical descriptive analysis})}$.

5.1.1 Participant Disposition

Participant disposition will include the number and percentage of participants who are screened, treated, completed the study as planned, participants withdrawn from the study, as well as the primary reason for early termination. Participant disposition will be summarized descriptively.

5.1.2 Analysis Populations

The number of participants included in each study population will be summarized descriptively. In addition, the inclusion of each participant into/from each of the defined analysis populations will be presented in the by-participant data listing.

6. **PROTOCOL DEVIATIONS**

Protocol deviations will be presented for each participant in the by-participant data listings.

Prior to database lock, all protocol deviations will be reviewed by medical monitors and assigned a status of Important if qualifying as such.

Protocol deviations and important protocol deviations will be categorized as noted in the protocol deviation management plan as per project and communication plan.

7. DEMOGRAPHIC AND BASELINE INFORMATION

Demographic and baseline information analysis will be based on the ITT population. Demographic and baseline information will be summarized descriptively as described in section 3.1 (Continuous/ Categorical)

Demographics

The following demographic parameters will be analyzed:

Continuous descriptive analysis:

- Age (years)
- Height (cm)
- Weight (kg)

Categorical descriptive analysis:

- Sex
- Childbearing Potential as defined in the protocol
- Race
- Ethnicity

Medical History

Medical history will be coded using MedDRA® and will be presented in the by-participant data listings.

Disease History

Disease history will be presented in a separate by-participant listing.

8. TREATMENT EXPOSURE

All study drug administration information (cohort, study drug administered <Yes/No>, date of injection, time of injection will be presented in the data listings.

9. PRIOR AND CONCOMITANT MEDICATIONS

Prior and concomitant medications will be coded using the most current version of the WHO-DD available at the start of the study.

Concomitant medications will be summarized for the safety population. by Anatomical Therapeutic Chemical (ATC) class Level 3 and Preferred name as noted in section 3.1 (categorical descriptive analysis). Participant who used the same medication on multiple occasions will only be counted once in the specific category (level and preferred name). ATC level and Preferred name will be presented alphabetically.

In addition to the summaries by the coded terms, the number of participants who used at least one concomitant medication during the study will be presented.

Prior medications will be presented in the by-participant data listings.

10. PHARMACOKINETICS

10.1 Plasma PK Analysis

The plasma PK samples for ONL1204 will be at specified times as follows:

- ٠
- Post-intravitreal injection
- 1-day post- intravitreal injection
- 3+ days post- intravitreal injection or day of surgery (vitrectomy)
- 14 days post-surgery
- Week 9
- Week 24 exit or early termination

All PK summary tables will be based on the plasma PK population. All analyses will be summarized as described in section 3.1 (PK - continuous descriptive analysis). All listings will be based on the safety population.

The following pharmacokinetic parameters will, where possible, be determined from the plasma concentrations of ONL1204 by non-compartmental method using Phoenix WinNonlin[®] software (Version 8.3 or higher):

Pharmacokinetic Parameters of Plasma ONL1204 Following a Single Dose Administration of ONL1204 Intravitreal Injection

Parameter	Definition
AUC0 last	The area under the plasma concentration time curve, from time 0 (time of dosing)
	to the last time point with measurable analyte concentration, calculated by the log
	down, linear up trapezoidal method
AUC0 inf	The area under the plasma concentration time curve from time 0 extrapolated to
	infinity. AUC0 inf is calculated as the sum of AUC0 last plus the ratio of the last
	measurable plasma concentration to the elimination rate constant (λz).
Cmax	Maximum analyte plasma concentration
Tmax	Time to maximum observed analyte concentration. If the maximum value occurs
	at more than one time point, Tmax is defined as the first time point with this
	value.
t ¹ /2	Apparent plasma terminal elimination half life calculated as $\ln (2)/\lambda z$

Parameter	Definition		
C _{max}	Maximum concentration which is directly determined from the plasma		
	concentration time profiles		
T _{max}	Time to maximum concentration. If the same C _{max} concentration occurs at		
	different time points, T _{max} is assigned to the first occurrence of C _{max} .		
AUC _{0-last}	Area under the drug concentration-time curve, from time zero to the last		
	measurable concentration using the 'Linear Up and Log Down' method		
AUC _{0-inf}	Area under the drug concentration-time curve, from time zero to infinity (∞) using		
	the following formula		
	$AUC_{0-\infty} = AUC_{0-t} + \frac{C_{t}}{\lambda_{z}}$		
	Where, C'_t is the observed concentration at the time t (last time point with a		
	measurable plasma concentration above the quantification limit) at which		
	quantification was still possible, the calculation of λ_z or k_{el} is given below.		

Parameter	Definition
AUC _{%extrap}	The percentage of the AUC that has been extrapolated beyond the last observed data point, using the following formula
	$AUC_{\%extrap} = \left(\frac{AUC_{0-\infty} - AUC_{0-t}}{AUC_{0-\infty}}\right) * 100$
λ_z or k_{el}	The apparent terminal elimination rate constant, will be estimated from a regression of $ln(C)$ versus time over the terminal log-linear drug disposition portion of the concentration-time profiles.
t _{1/2}	Apparent terminal half-life, using the following formula
	$T_{1/2} = \frac{Ln(2)}{\lambda_z}$
CL/F	Apparent total plasma clearance, using the following formula
	$CL/F = \frac{D}{AUC_{0-\infty}}$
	Where $D = Administered$ dose; $AUC_{0-\infty} = AUC_{0-inf}$
V _z /F	Apparent terminal volume of distribution, using the following formula
	$V_z/F = rac{CL/F}{\lambda_z} \ Or \ rac{Dose}{\lambda_z \times AUC_{inf}}$

Value for K_{el} , $t^{1/2}$ AUC_{0-inf}, CL/F and V_z/F will not be reported for cases that do not exhibit a terminal log-linear phase in the concentration versus time profile. Additional pharmacokinetic parameters may be determined where appropriate.

Pharmacokinetic analysis will be carried out using actual doses, infusion durations, and blood sampling times, where possible. If actual times are missing, nominal times may be used with sponsor approval.

Plasma concentrations of ONL1204 will be used as supplied by the bioanalytical laboratory. The units of concentration and resulting PK parameters, with amount or concentration in the unit, will be presented as they are received from the bioanalytical laboratory.

10.1.1 Criteria for the Calculation of an Apparent Terminal Elimination Half-Life and AUC

The start of the terminal elimination phase for each participant will be defined by visual inspection and will generally be the first point at which there is no systematic deviation from the log linear decline in plasma concentrations.

10.1.1.1 Number of Data Points

• At least 3 data points will be included in the regression analysis and not including Cmax.

10.1.1.2 Goodness of Fit

- If data permits, the default 'best fit' method by Phoenix WinNonlin will be used for the selection of slopes to determine ' λz '. If data do not permit, then the slope selection will be done by visual inspection or by a manual method to determine λz considering the best possible the adjusted R² value.
- When assessing terminal elimination phases, the adjusted R² value will be used as a measure of the goodness of fit of the data points to the determined line.
- Regression-based parameters (K_{el} , $t^{1/2}$ AUC_{0-inf}, CL/F and V_z /F AUCinf, t1/2, CL, and V_z) will only be calculated if the adjusted R² value of the regression line is greater than or equal to 0.7. If regression-based parameters cannot be calculated, they will be set to "NC", defined as "not calculated" in the data listings and summary tables as appropriate.

10.1.1.3 Period of Estimation

- Time period used for the estimation of t1/2, where possible, will be over at least 2 half lives.
- Where an elimination half life is estimated over a time period of less than 2 half lives, it will be flagged in the data listings at the discretion of the pharmacokineticist, and the robustness of the half life value and regression based parameters (AUC0 inf, CL, and Vz) should be discussed in the study report.

10.1.1.4 Calculation of AUC

- The minimum requirement for the calculation of AUC will be the inclusion of at least 3 consecutive plasma concentrations above the lower limit of quantification (LLOQ), with at least one of these concentrations following C_{max} .
- All AUC values will be calculated using the 'linear up / log down' trapezoidal rule where the linear trapezoidal rule will be used for increasing concentrations and the log trapezoidal rule for decreasing concentrations.

Pharmacokinetic Noncompartmental Analysis (NCA)

10.1.2 General Plasma NCA Pharmacokinetic Settings

•	NCA Model Type	Plasma (200-202)
•	Weighting	Uniform
•	AUC Calculation Method:	Linear Up/Log Down
•	Dose Options Type	Extravascular
•	Slopes Setting Fit Method:	Best Fit. If the data does not permit best fit selection, the slope selection will be performed by visual inspection or by a manual method to determine λ_z .
•	Rsq_Adjusted Criteria for 'λz'	0.70
•	AUC% extrapolation Criteria	20

